ALLIANCE FOR CLINICAL TRIALS IN ONCOLOGY

PROTOCOL UPDATE TO CALGB 30610

PHASE III COMPARISON OF THORACIC RADIOTHERAPY REGIMENS IN PATIENTS WITH LIMITED SMALL CELL LUNG CANCER ALSO RECEIVING CISPLATIN OR CARBOPLATIN AND ETOPOSIDE

- | | |
|--|---|
|  Update: |  Status Change: |
|  Eligibility changes |  Activation |
|  Therapy / Dose Modifications / Study Calendar changes |  Closure |
|  Informed Consent changes |  Suspension / temporary closure |
|  Scientific / Statistical Considerations changes |  Reactivation |
|  Data Submission / Forms changes | |
|  Editorial / Administrative changes | |
|  Other | |

Expedited review is allowed. IRB approval (or disapproval) is required within 90 days. Please follow your IRB of record guidelines.

UPDATES TO THE PROTOCOL:

Cover Page

The Respiratory Committee Chair has been updated from [REDACTED]
A new Staff Statistician has been added.
The Data Manager has been updated from [name] to [name].

CTSU Address and Contact Information Page

The information under “Submit study data to” has been updated.

Section 4.3 Prior Treatment

The 4th sentence of the first bullet point: “Registration to CALGB 30610 must take place within 7-21 days after the start of the non-protocol therapy” has been moved to Section 5.4 of the registration section. This is no longer in the eligibility section.

Section 5.0 Patient Registration

The entire section has been modified with the updated CTSU language.

Section 5.5 Stratification

The radiotherapy start time language has been clarified.

Section 6.1 Data Submission

The first four paragraphs in this section have replaced the previous data submission language. In the paragraph following the table information about using CTCAE version 5 for **serious** AE reporting has been added.

Section 16.0 Adverse Event Reporting

The references to the CTCAE reporting have been updated from version 4.0 to version 5.0 for serious AE reporting. CTCAE version 4.0 will continue to be used for routine AE reporting.

Section 16.2 Additional Instructions or Exclusions from CTEP-AERS Expedited Reporting Requirements

1.0 INTRODUCTION

The integration of thoracic radiotherapy (TRT) with systemic chemotherapy for the treatment of limited-stage small cell lung cancer (LSCLC) has been widely studied. Two meta-analyses, published in the early 1990s, confirmed that adding TRT to chemotherapy significantly improved long-term survival for patients with LSCLC [1, 2]. A recent overview of prospective research in LSCLC included 26 randomized clinical trials initiated by cooperative groups in North America between 1972 and 1992 and only 5 studies showed statistically significant survival prolongation in the experimental arm compared with the control arm [3]. All five positive trials studied some aspect of TRT. Although several important questions remain unanswered regarding the optimal integration of TRT and chemotherapy in LSCLC, an Intergroup phase III study addressing limited stage small cell lung cancer study has not been conducted in more than 13 years.

1.1 Thoracic Radiotherapy

Traditionally, modest total doses of radiation, ranging from 45–50 Gy, were employed because of the observed responsiveness of small-cell lung cancer to radiotherapy [4]. Although high clinical response rates are expected with combined modality therapy, durable local tumor control is poor when modest-dose, conventionally fractionated TRT is employed. For example, intrathoracic tumor relapse was observed in the majority of patients treated with 45 Gy once-daily (QD) radiotherapy concurrent with cisplatin and etoposide chemotherapy in a modern prospective phase III trial [5].

Intensifying the radiotherapy course by accelerating the time to complete treatment (while maintaining the same nominal total radiation dose) appears to be an effective strategy in LSCLC. Intergroup trial 0096 (INT 0096) randomized patients to either conventional (180 cGy QD x 25 fractions [45 Gy in 5 weeks]) or hyperfractionated, accelerated (150 cGy twice daily (BID) x 30 fractions [45 Gy in 3 weeks]) TRT [5]. TRT was initiated with the first cycle of etoposide/cisplatin (PE) chemotherapy. Mature results of this trial demonstrate statistically significant improvement in overall survival for the accelerated TRT. Five-year survival was 26% with accelerated RT compared with 16% for patients receiving conventional TRT. Patterns of recurrence reflected improved local and local plus distant recurrence rates with accelerated TRT, suggesting that local treatment has a significant impact on ultimate outcome in LSCLC. The cumulative rate of local tumor relapse was 75% with once-daily TRT compared with 42% with twice-daily TRT. The major increased toxicity of the accelerated regimen was a doubling of the grade 3/4 acute esophagitis rate (e.g., 16% vs 32%).

INT 0096 was a well-conducted phase III study demonstrating that altering the administration of radiotherapy could ultimately influence survival. Despite this result, the 45 Gy BID TRT regimen has not been well accepted in clinical practice. The Patterns of Care Study published in 2003 noted that fewer than 10% of patients with LSCLC received this regimen, while more than 80% were treated with QD TRT [6]. In addition, recent phase II cooperative group trials in LSCLC have not routinely employed 45 Gy BID TRT. The reluctance to accept accelerated TRT may be in part due to increased acute toxicity and practical issues involved with treating patients twice each day. However, the results of the study have also been questioned due to the inclusion of 45 Gy QD TRT as the standard treatment. The predicted biologic efficacy of 45 Gy QD TRT is poor, and a high dose QD TRT arm (e.g., ≥ 60 Gy), which is commonly employed in clinical practice, was not included in the INT 0096 study.

Alternative strategies for increasing the efficacy of treatment include administering either high dose QD TRT, or giving concomitant boost therapy, where BID treatment is given only during part of the treatment course. The Cancer and Leukemia Group B (CALGB) has extensively studied high-dose QD TRT. CALGB 8837, a phase I study, was designed to determine the maximum-tolerated dose (MTD) of TRT in both standard QD and accelerated BID schedules

[7, 8]. Chemotherapy consisted of three cycles of cisplatin, cyclophosphamide, and etoposide followed by two cycles of cisplatin plus etoposide. TRT was initiated with the 4th cycle of chemotherapy, although the initial treatment volume (e.g., lung volume receiving 40 Gy) included the extent of disease at diagnosis. The TRT volume was reduced to include only the post-chemotherapy volume following 40 Gy. The MTD of BID RT was determined to be 45 Gy in 30 fractions over 3 weeks, while it was judged to be at least 70 Gy in 35 fractions over 7 weeks for daily RT. The median survival for QD TRT was 29.8 months compared with 24 months for BID TRT, and 36% of patients treated with high dose QD RT were alive 6 years after therapy compared with 20% for BID RT. Although the number of patients was small, a dose response was also suggested for patients receiving high dose QD TRT. A subsequent CALGB phase II study (C 39808) employed 70 Gy thoracic RT concurrent with carboplatin and etoposide following 2 cycles of induction paclitaxel and topotecan chemotherapy [9]. This Group-wide study confirmed the feasibility of delivering 70 Gy TRT. The overall toxic effects of therapy were comparable with other recent trials using more modest total doses of TRT, and the incidence of severe esophagitis appeared reduced compared with reports of accelerated TRT. Although a larger proportion of patients on C 39808 had weight loss > 5% prior to enrolling on study (33% versus 18%), outcomes were comparable to the accelerated TRT arm of INT 0096. Moreover, median survival on C 39808 was 31 months when the population was limited to patients with weight loss < 5% prior to diagnosis. Two additional CALGB phase II trials employing 70 Gy TRT have completed accrual, further confirming the acceptance of this regimen.

The Radiation Therapy Oncology Group (RTOG) has studied a concomitant boost (CB) strategy in LSCLC. Concomitant boost radiotherapy has been shown to improve local tumor control in head and neck squamous cell carcinoma compared with standard radiotherapy [10]. The concomitant boost regimen has been accepted in clinical practice for head and neck cancer, which is demonstrated in part by rapid accrual to recent studies combining concomitant boost radiotherapy with chemotherapy (RTOG 0129 and RTOG 0522). This approach allows acceleration of TRT but only requires hyperfractionated TRT during part of the treatment course. Moreover, BID large field TRT can be avoided. A phase I trial has been completed assessing the MTD for concomitant boost TRT in LSCLC (R 9712). TRT was initiated with the first of 4 cycles of PE chemotherapy. Accelerated TRT, 61.2 Gy in 34 fractions of 1.8 Gy/Fx in 5 weeks, with BID TRT during the final 9 treatment days, was determined to be the maximum tolerated dose (MTD) [11]. A subsequent phase II study, RTOG 0239, employs the 61.2 Gy concomitant boost regimen and recently completed accrual [12].

The efficacy of radiotherapy can be predicted by calculating the biologic effective dose (BED) [13]. The BED reflects the tumor type (doubling time), dose per fraction, nominal total dose and may also take into account the time to complete therapy. In comparison to the accelerated 45 Gy BID regimen studied in INT 0096, both the CALGB TRT regimen of 70 Gy QD and the RTOG concomitant boost approach yield substantially higher BEDs. For example, assuming a potential tumor doubling time of 5 days, the predicted increase in BED would range from 1.3 to 1.6 (e.g., 30% to 60% increase in efficacy) for the CALGB and RTOG experimental regimens compared with 45 Gy BID.

Predicted Biologic Effective Dose (BED) of Thoracic Radiotherapy Regimens

TRT Regimen	Nominal Dose	BED	BED _{-Time}	Relative BED
INT 0096: 45 Gy (1.5 Gy BID/3 weeks)	45 Gy	52	43	1.0
CALGB: 70 Gy (2.0 QD / 7 weeks)	70 Gy	84	63	1.4 – 1.6
RTOG: 61.2 Gy (1.8 Gy CB / 5 weeks)	61.2 Gy	72	57	1.3 – 1.4

Given the impact of intensified local therapy seen in INT 0096, evaluation of TRT regimens that have the potential to further enhance local tumor control and survival is warranted. Importantly, the experimental regimens may be better tolerated and more practical to deliver than the 45 Gy BID regimen. A positive outcome, reflecting an enhanced therapeutic ratio, should result in widespread acceptance in clinical practice.

1.2 Timing of Radiotherapy

The optimal timing of TRT relative to chemotherapy remains controversial. CALGB 8083 randomly assigned patients to receive initial RT plus chemotherapy, delayed RT plus chemotherapy, or chemotherapy alone [14]. Chemotherapy consisted of cyclophosphamide, etoposide, and vincristine, with doxorubicin substituting for etoposide during later cycles. RT, 50 Gy in five weeks, was administered with the 1st cycle (early) or 4th cycle (delayed) of chemotherapy. Mature results showed that survival with chemotherapy alone was inferior to both TRT arms, and the difference was statistically significant for delayed TRT ($p=.002$) and approached significance for early TRT ($p=.082$). No significant difference was observed between early and delayed RT, although there was a trend favoring delayed TRT ($p=0.14$). Conversely, a phase III trial from the National Cancer Institute of Canada (NCIC) demonstrated a benefit for initiating RT, 40 Gy in 3 weeks, with the 2nd chemotherapy cycle compared with the 6th cycle of chemotherapy [15]. Five-year survival was 20% in the early TRT cohort compared with 11% in the late TRT arm, and the difference was ascribed to a reduction in brain metastases, as local tumor control did not differ between arms. Additional studies have attempted to address the timing of TRT, including a trial from Japan comparing 45 Gy BID TRT during the first cycle of chemotherapy with the same TRT regimen administered following the completion of chemotherapy [16]. Median survival was 27 months with early (concurrent) TRT and 20 months with late (sequential) TRT, and the difference approached statistical significance. Recent meta-analyses have been published addressing this issue [17, 18]. While definitive conclusions cannot be reached, there is general consensus that the early initiation of TRT (e.g., cycle 1-3) may be beneficial, particularly in the context of intensive TRT.

Given that the available evidence supports administration of thoracic radiotherapy with either the first or second cycle of systemic chemotherapy, the study was amended on September 15, 2009. Investigators now choose when radiotherapy will start at the time of patient registration. This will allow additional time for investigators to perform sophisticated radiotherapy treatment planning in select patients without delaying the administration of chemotherapy. The timing of radiotherapy delivery (e.g. cycle 1 vs cycle 2) will be incorporated as a stratification factor. Additionally, as of February 20, 2013, patients will be allowed to receive one cycle of chemotherapy prior to registering on CALGB 30610. These patients will then receive the radiotherapy during their second cycle of chemotherapy (their first cycle of protocol therapy).

1.3 Chemotherapy

SCLC is exquisitely sensitive to systemic chemotherapy with high overall response rates. The combination of cisplatin and etoposide (PE) became standard front-line therapy in the 1980s given its clinical activity and tolerability in combination with concurrent thoracic irradiation. PE proved to be at least equivalent to previous combinations including cyclophosphamide, doxorubicin, and vincristine [19, 20]. Recent attempts to find more efficacious regimens by either adding or substituting agents have been disappointing. A phase III CALGB trial compared paclitaxel/etoposide/cisplatin (PET) with PE as first-line therapy for extensive SCLC [21]. Median survival was similar in both arms (5.9 versus 6 months), but toxic deaths increased from 2.4% with PE to 6.5% with PET. The RTOG conducted a phase II study of PET chemotherapy in LSCLC. TRT, 45 Gy BID, was given concurrent with the first of 4 cycles of PE. While the regimen was active, the authors of the study concluded that the addition of paclitaxel was unlikely to improve survival in LSCLC [22]. The topoisomerase-I inhibitors, topotecan and irinotecan, are active agents against SCLC. Topotecan has been studied in combination with paclitaxel in both extensive and limited SCLC, but phase II trials did not suggest improved outcomes that would warrant study in a phase III setting [23]. In contrast, irinotecan plus cisplatin (IP) was superior to PE in a phase III study for extensive SCLC conducted by the Japanese Cooperative Oncology Group [24]. Confirmatory trials were subsequently designed in North America comparing PE to IP. The preliminary results of the initial confirmatory study were recently reported and there was no statistically significant difference in median time to progression, median survival or 1-year survival between the EP and IP regimens [25]. A second phase III trial testing IP vs PE, coordinated by the Southwest Oncology Group, is ongoing, although the results may not be available in the near future. At this time, there is not an obvious hypothesis regarding the integration of novel systemic therapy that would merit testing in a phase III setting. Importantly, it is necessary to define an optimal TRT regimen for the design of future studies that may test the merit of novel cytotoxic agents and molecular targeted agents.

1.4 High Dose Thoracic Radiotherapy Concurrent with Cycle 1 Chemotherapy

RTOG 0241/CALGB 30202 is a recent experience administering high dose QD TRT during the initial cycle of chemotherapy in LSCLC [26]. This phase I study evaluated 70 Gy TRT in combination with cisplatin (60 mg/m² day 1) and escalating doses of irinotecan. As noted in the table below, 2 dose limiting toxicities have been observed out of 15 patients assigned to receive 70 Gy TRT; one grade 4 diarrhea and one grade 4 esophageal spasm.

Although TRT was not administered until the 4th cycle of chemotherapy in CALGB 8837, the initial 40 Gy was delivered to the pre-chemotherapy thoracic tumor volume as measured on the CT scan obtained at the time of trial entry. Thus, an increased volume of functioning lung was irradiated on this trial compared with an approach of immediate chemoradiotherapy. Despite treating the pre-chemotherapy lung volume to 40 Gy, grade 3+ pulmonary toxicity was not encountered.

Prospective trials of locally advanced non-small cell lung cancer provide substantial additional experience integrating high dose QD TRT with cycle 1 chemotherapy. TRT doses ranging between 61 Gy to 74 Gy given in 6.5 to 7.5 weeks have been administered with various chemotherapy regimens (table). The proposed study will mandate early interim analyses of both experimental treatment arms for assessment of treatment related toxic effects of therapy.

Selected Lung Cancer Trials: High Dose Daily Thoracic RT Concurrent with Cycle 1 Chemotherapy

Study	n	Dose/ # fractions	Chemotherapy	Toxic Effects	
				Gr 5 (any)	Gr 3/4 esph Gr 3/4 dysp
RTOG 0241/ CALGB 30202 (26) (phase I LSCLC)	15	70 Gy/35 fx	Cisplatin + Irinotecan	Gr 5 (any)	0%
				Gr 3/4 esph	14%/7%
				Gr 3/4 dysp	7%/0%
RTOG 0117 (27) (phase I/II NSCLC)	39*	74 Gy/37 fx	Carboplatin + Paclitaxel	Gr 5 (any)	5%
				Gr 3/4 esph	15%/0%
				Gr 3/4 dysp	5%/0%
CALGB 30407 (28) (phase II NSCLC)	26*	70 Gy /35 fx	Pemetrexed + Carboplatin	Gr 5 (any)	4%
				Gr 3/4 esph	15%/0%
				Gr 3/4 dysp	4%/4%
CALGB 39801 (29) (phase III NSCLC)	121	66 Gy/ 33 fx	Carboplatin + Paclitaxel	Gr 5 (any)	1%
				Gr.3/4 esph	29%/1%
				Gr 3/4 dysp	9%/2%
RTOG 9410 (30) (phase III NSCLC)	201	63 Gy/34 fx	Cisplatin + Vinblastine	Gr 5 (any)	2%
				Gr 3/4 esph	25%
				Gr 3/4 dysp	11%
SWOG 9504 (31) (phase II NSCLC)	83	61 Gy/33 fx	Cisplatin + Etoposide	Gr 5 (any)	4%
				Gr 3/4 esph	12%/5%
				Gr 3/4 dysp	5%/0%
SWOG 0023 (32) (phase III NSCLC)	473	61 Gy/ 33 fx	Cisplatin + Etoposide	Gr 5 (any)	3%
				Gr 3/4 esph	14%/1%
				Gr 3/4 dysp	3%/1%

NSCLC = non-small cell lung cancer, Gr = grade, esph = esophagitis, dysp= dyspnea

1.5 Summary

In summary, defining an optimal TRT regimen in LSCLC remains critical and will have a major impact on clinical practice. Intergroup study 0096 clearly established that improving the efficacy of thoracic radiotherapy can significantly impact survival in patients with LSCLC. Given the reluctance for practitioners to adopt 45 GY BID TRT, the validity of this regimen needs to be assessed in the context of TRT regimens that have higher predicted biologic efficacy and may have improved tolerability and acceptance. Superior outcomes on an experimental arm would lead to establishing a change in the standard of care for patients with LSCLC. Conversely, if the best outcomes were observed with accelerated 45 Gy BID TRT, then the results of this study would provide convincing and definitive evidence for practitioners to adopt this regimen.

As of December 15, 2012, this trial was updated to include only 2 arms. The Alliance Data Safety and Monitoring Board (DSMB) reviewed adverse events for CALGB 30610 on June 29, 2012. At that time the trial had reached sufficient accrual to trigger a decision regarding dropping one of the experimental arms. Toxicity in the 2 arms was found to be similar in the review, and the DSMB unanimously recommended that the Respiratory Committee decide which arm should continue in conjunction with CTEP. The Alliance Respiratory Committee subsequently reviewed the toxicity data and it was noted that while overall toxicity was similar, three on-study deaths (4.5%) were observed in arm C compared with no on-study deaths in arm B. Based on this review and the study mandate to eliminate one treatment arm, the Alliance Respiratory

Committee proposed dropping arm C. This decision was supported after review and discussion with CTEP representatives.

As of September 15, 2014, the protocol was amended to allow substitution of carboplatin for cisplatin at the discretion of the treating physician, and the choice of chemotherapy will be used as a stratification factor. It has become clear during the past several years that carboplatin and etoposide chemotherapy is a commonly used regimen for patients with limited small cell lung cancer, and several investigators have requested that a carboplatin based regimen be allowed. Though the choice of chemotherapy has been widely discussed, there is not clear data that supports the use of cisplatin over carboplatin in small cell lung cancer. A study randomizing patients with small cell lung cancer to receive either cisplatin or carboplatin (with etoposide), conducted by the Hellenic Cooperative Oncology Group, did not demonstrate a difference in response rates or survival with either regimen (99). Moreover, phase II CALGB studies employing a carboplatin and etoposide backbone concurrent with high dose (7000 cGy) thoracic radiotherapy have accrued well.

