8.0 TREATMENT PLAN

Patients registered to CALGB 30610 prior to the start of cycle 1 protocol treatment will start therapy within 7 days of registration.

Questions regarding treatment should be directed to the Alliance Study Chair.

Protocol therapy will consist of 4 cycles of cisplatin and etoposide or carboplatin and etoposide chemotherapy administered every 21 days. Thoracic radiotherapy will begin either on the first day of the first cycle of chemotherapy OR on the first day of the second cycle of chemotherapy.

Patients may be registered to CALGB 30610 following one cycle of chemotherapy. Patients must receive the second cycle of therapy following registration, on day 22-24, so that the patient adheres to a 3-week treatment cycle. Patients not able to be treated within 3 days of day 22 should not be registered to CALGB 30610. For patients registered to CALGB 30610 after 1 cycle of chemotherapy, the thoracic radiotherapy must begin with the second cycle of chemotherapy (the first cycle of protocol chemotherapy after the patient was registered). Additionally, the cycle of chemotherapy given prior to registration will be considered “cycle 1.” Therefore, patients registered following 1 cycle of chemotherapy will receive three cycles of therapy after registration.

The original design was a randomized phase III trial including two experimental treatment arms (70 Gy once daily radiotherapy and 61.2 Gy concomitant boost radiotherapy) and a standard treatment arm (45 Gy twice daily radiotherapy). An interim analysis, conducted after accrual of a pre-determined number of patients, selected one experimental arm based upon a comparison of treatment related toxicity. The most toxic experimental arm, which was Arm C, was discontinued, and the trial now compares standard therapy to the selected experimental regimen.

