In the initial stage of the study, eligible patients will be randomized to arms 1, 2 and 3 with probability ratio of 1:1:1. A blocking design with 30/30/30 patients will be used to compare toxicity between the experimental arms. Specifically, after 30 patients have been accrued to each experimental arm, the Alliance Statistics and Data Center will computerize and analyze all treatment related toxicities and report findings to the study team and the DSMB. For the 60 patients treated by experimental regimens, permutation t test will be used to compare toxicity severity scores between experimental arms. If the 2-sided p value of the permutation test is less than 0.05, a decision will be made to drop the experimental arm with higher toxicity; otherwise, the study will continue and adverse events will be analyzed again after 20 additional patients have been treated in each experimental arm. For the 100 patients treated by experimental regimens so far, if statistically significant difference of adverse events is found between the experimental arms, a decision will be made to drop the

experimental arm with higher toxicity; otherwise, the study will continue after 20 additional patients have been treated in each experimental arm. For the first 140 patients treated by experimental regimens, the experimental arm with the highest cumulative numerical toxicity score will be discontinued following review by the study team and the DSMB.

A notice will be broadcast to all Alliance and CTSU institutions for the discontinuation of an experimental arm. In the initial stage of the trial, while the toxicity profiles of treated patients are being evaluated, the study accrual will not be suspended. In the second stage, the study will proceed with the remaining experimental arm and the standard treatment arm with 1:1 allocation.

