15.4 Analysis Plan Including Plans for Formal Interim Analysis

Both short term and long term toxic effects of therapy will be captured and monitored closely. Severe toxic events will be reported and monitored as per NCI guidelines for clinical studies (e.g., CTEP-AERS). These data will be critical in the assessment of each of the treatment regimens. In addition, the Alliance DSMB will perform a formal review of the available data at each of its semiannual meetings. This review will include both acute and late toxicity.

After discontinuing one of the experimental arms with worse toxicity profile, in the second stage of the study, the first formal interim analysis for efficacy will occur once 78 deaths are observed in the remaining study arms. After that, formal interim analyses will be conducted annually, with the final analysis at year 8.5, corresponding to approximately 140, 213, 292, 374, 437 and 483 deaths. The trial is subject to stopping early for either superiority or inferiority of the experimental relative to the standard arm if either arm was markedly superior in terms of overall survival. The main reason is that if both arms were roughly equal in terms of overall survival, the final conclusion might be to recommend the experimental arm for future use because of less toxicity or more convenience. Using S+SeqTrial [83], we will construct two-sided symmetric monitoring boundaries in the spirit of O'Brien and Fleming [84]. To maintain overall 1-sided alpha level of 0.025 for each boundary and be conservative in the initial looks, we will truncate alpha level at 0.0005 for the first look and at 0.0025 for other interim looks [85]. The final analysis at 8.5 years after study activation will conclude superiority (inferiority) of the remaining experimental arm to the standard arm if the p-value of a one-sided log rank test for superiority (inferiority) is less than 0.0220. The following table displays the operating characteristics, including power, average study size, stopping probabilities under true hazard ratios of 0.75, 1.0, 1.3, and 1.5. The exact performance of the study design, especially under different allocation ratios in the first and the second stage of the study, will be investigated using simulation.

Hazard Ratio ($\lambda_1/\lambda_{2/3}$)	Expected Number of Deaths	Prob. to Reject $H_0: \lambda_1 / \lambda_{2/3} = 1$ (Power)	Early Stop Prob. for Superiority	Early Stop Prob. for Inferiority
0.75	354	0.8763	0.0000	0.6348

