Contingency tables will be used to summarize the frequency of toxicity by severity, type and treatment. For comparison of the frequency of toxic events, the Cochran-Mantel-Haenszel test will be used to take advantage of the trend effect among toxicity grades.

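### The 70 Gy arm was kept partly on its early safety record, and those patients also count in the final toxicity comparison with 45 Gy; the resulting tilt toward 70 Gy is small, mainly in fatal events, and needs a sensitivity table

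*Combined protocol and SAP*

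**What the plan says.** Section 15.1.2 sets up a choice between the two experimental arms on acute toxicity. If neither of the first two looks is significant, then at 140 experimental-arm patients "the experimental arm with the highest cumulative numerical toxicity score will be discontinued following review by the study team and the DSMB".

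Section 1.5 describes what happened. Of the DSMB review of June 29, 2012 it says "Toxicity in the 2 arms was found to be similar in the review". The Respiratory Committee then noted that "three on-study deaths (4.5%) were observed in arm C compared with no on-study deaths in arm B". Citing that finding together with the obligation to remove one of the arms, the committee put forward arm C for discontinuation, and CTEP representatives supported this. Section 8.0 gives a different account: "The most toxic experimental arm, which was Arm C, was discontinued".

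Section 15.3 plans 303 patients on 45 Gy and 303 on 70 Gy. It records 88 randomized to the dropped arm and a total accrual of 729 with a 5% allowance.

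For the toxicity analysis, section 15.4 says "For comparison of the frequency of toxic events, the Cochran-Mantel-Haenszel test will be used". It names no analysis population and makes no provision for the patients used in the arm choice. The same section explains the symmetric stopping boundaries by saying that, if survival were roughly equal, "the final conclusion might be to recommend the experimental arm for future use because of less toxicity or more convenience".

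**The concern.** When the better-looking of two arms is kept, its early results are on average better than its true rate. If those patients are then pooled into a comparison with a third arm that was never at risk of being dropped, the pooled rate of the kept arm is biased in its favour.

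Here the early results were safety results, and the later comparison is also on safety. Comparing toxicity is objective 2.2.1, and section 15.4 names lower toxicity as one possible ground for recommending 70 Gy if survival is similar. Fatal events are few, so a shift of one or two can change how the grade 5 row reads.

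There is also a conflict of wording. Section 8.0 says the choice rested on treatment-related toxicity and calls arm C the most toxic. Section 1.5 says toxicity was similar and cites on-study deaths, without attributing them to treatment and without reporting the section 15.1.2 score.

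**Working it through.** **1. Size of the selection cohort.** Input: 3 deaths = 4.5% in arm C (section 1.5). 3/66 = 4.55% and 3/67 = 4.48% both round to 4.5%; 3/65 = 4.6% and 3/68 = 4.4% do not. Arm C therefore had 66 or 67 patients in that review. No denominator is printed for arm B; about 67 is an assumption resting on the 1:1:1 allocation in section 15.3.

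**2. Are these patients inside the 303?** 303 + 303 + 88 = 694, and 694 × 1.05 = 728.7, which is the stated 729. The total is reached only if stage 1 patients on 45 Gy and 70 Gy are part of the 303s. The cohort is then 67/303 = 22% of the 70 Gy arm, or 88/303 = 29% if selection used as many as were finally randomized to arm C.

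**3. How strong was the evidence at the choice?** For 3/67 vs 0/67 the two-sided Fisher p is 0.24. The upper 97.5% limit for 0/67 is 1 − 0.025^(1/67) = 5.4%.

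**4. Bias in deaths if deaths drove the choice.** Assume one true on-study death rate in all arms, p = 3/134 = 2.2%, with 67 per experimental arm at selection.
- Expected deaths without selection: 303 × 3/134 = 6.8, of which 67 × 3/134 = 1.5 fall in the cohort.
- Keeping the arm with fewer deaths (simulation): the kept cohort averages 0.85 deaths. The total is 0.85 + 236 × 3/134 = 6.1, a shortfall of 0.65 (10%).
- Given the observed zero: 236 × 3/134 = 5.3, a shortfall of 1.5 (22%).
- Over assumed true rates of 1% to 4.5%, the average bias in the pooled rate is 0.14 to 0.31 percentage points. Given the zero it is about 0.2 to 1.0 points, or 0.7 to 3 deaths.

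**5. Error of a test on death rates (same 2.2% scenario, nominal one-sided 2.5%).** A z-test favours 70 Gy in 3.7% of trials and 45 Gy in 1.6%. With about six events per arm the z-test is a poor approximation. Fisher's exact test favours 70 Gy in 1.8%, against 1.2% without selection. Only conditioning on the observed zero takes it above nominal, to about 3.3%.

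**6. Error of a test on toxicity grades.** This is closer to the planned analysis. Patients were scored 0 to 3 as in section 15.1.2, under three assumed distributions with 2.25% grade 5 in each; equal truth, 303 vs 303, nominal one-sided 2.5%.
- Selection on deaths, 67 per arm: bias 0.005-0.006 SD, error about 2.9-3.0%. The share scoring 2 or 3 moves by less than 0.1 point.
- Selection on the full score: bias = (67/303) × 0.564/√67 = 0.015 SD, which is 0.015/√(2/303) = 0.19 standard errors. Error is about 3.5-3.8% over 67 to 88 per arm.
- Leaving out the selection cohort brings the error back to about 2.5%.

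**7. Survival.** A shift of 0.65 deaths among 483 moves z by about 0.65/√483 = 0.03. A nominal 0.025 becomes about 0.027.

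**The case against.** The strongest objection is size. The planned test runs across toxicity grades, and selection on deaths hardly moves grades 3 and 4. The 3.7% for death rates comes from a z-test on about six events per arm and falls below nominal under an exact test. The higher grade-test error applies only if the section 15.1.2 score drove the choice, and section 1.5 reports no score. All of this stands, and it limits the point to a modest bias concentrated in fatal events.

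A second objection is that on-study deaths need not be toxic deaths. Section 1.5 gives no attribution, so the link to the grade 5 toxicity row is an assumption. Reuse of the cohort is likewise inferred from the accrual arithmetic, because section 15.4 names no toxicity population.

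Third, a reader might infer that section 8.0 is simply wrong to call arm C the most toxic. The documents do not show that. The last-look rule needs only a numerically higher score, not significance, so p = 0.24 does not refute it. If the three deaths were grade 5 toxicities they would add 3 × 3 = 9 points to arm C. Overall similarity and a higher score can both be true. What remains is two accounts that do not match.

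Fourth, a reader might infer that the tilt could decide the recommendation. Section 15.4 only says that toxicity might count, offers convenience as an alternative ground, and sets no toxicity decision rule.

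**Conclusion.** The mechanism holds and its direction is toward 70 Gy. The arm was chosen on early safety information, its early patients count again by the plan's own arithmetic, and no adjustment is planned. The size is small: on average about 0.65 of 6.8 expected deaths, about 1.5 given the observed zero, and one-sided error in a grade-based test of about 2.9-3.0% (choice on deaths) or 3.5-3.8% (choice on the score) instead of 2.5%. The overall survival comparison is essentially unaffected.

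These figures assume equal true rates in the arms, a 2.2% death rate, assumed score distributions and about 67 arm B patients at selection. It would go too far to say that 70 Gy was kept solely because of the zero deaths: section 1.5 cites the review together with the obligation to drop one arm. The point supports a cheap improvement; it does not show that the toxicity comparison is invalid.

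**What to change.** In section 15.4, name the toxicity analysis population and keep the all-patient comparison as the main analysis. Add a sensitivity analysis with the same Cochran-Mantel-Haenszel test, plus grade 5 and on-study death rates, for 45 Gy and 70 Gy patients randomized after the selection cohort. Define that cohort by the actual data cut behind the arm decision: June 29, 2012 is a review date, no cut date is printed, and the committee looked at the data afterwards. Report this table beside any statement that 70 Gy is less toxic, but do not make it a condition for that statement.

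Reconcile section 8.0 with section 1.5, so that both give the same basis for dropping arm C. If the section 15.1.2 scores were calculated, report them.

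The cost is one table and a few sentences. With 67 per arm removed, 236 per arm remain: 22% fewer patients and intervals √(303/236) = 1.13 times as wide. Power in that table is lower. For an assumed 32% vs 22% toxicity rate it falls from 79% to 69%, which is why the table should support the main analysis and not act as a gate.
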